#### **9.4.1.2 Sensitivity Analyses for the Primary Endpoint**

Additional sensitivity analyses of the primary endpoint may be defined in the SAP.

#### **9.4.1.3 Subgroup Analyses for the Primary Endpoint**

Subgroup analyses will be conducted for the primary efficacy endpoint for the FAS using the analysis described in [Section 9.4.1](#) and the imputation methods described in [Section 9.4.1.1](#). Subgroups to be evaluated will include the following:

- Gender
- Age categories at the time of randomization (< 65 years; ≥ 65 years)
- Race
- Baseline 24-hour UPCR (Visit A4) (< 3.0 mg/mg; ≥ 3.0 mg/mg)
- Total cumulative IV corticosteroid (methylprednisolone or parenteral equivalent) dose given in the 16 weeks before randomization (< 250 mg; ≥ 250 mg)

Additional subgroups defined for descriptive summaries will be specified in the SAP.

#### **9.4.2 Secondary [REDACTED] Efficacy Endpoint Analyses During Week 52 (Part B)**

Binary efficacy endpoints (responder/nonresponder) will use stratified Cochran-Mantel-Haenszel (CMH) tests stratified by the factors used for randomization (UPCR < 3.0 mg/mg vs ≥ 3.0 mg/mg) and total cumulative IV corticosteroid (methylprednisolone or parenteral equivalent) dose given in the 16 weeks before randomization (< 250 mg versus ≥ 250 mg) to compare the response rates of BMS-986165 (combined BMS-986165 treatment groups) to placebo for the FAS. Nominal p-values will be provided.

Treatment differences in response rates and the corresponding 2-sided 95% CIs for the difference in proportions between the combined BMS-986165 treatment groups and placebo will be provided. Additionally, treatment differences in response rates and corresponding 95% CIs for the difference in proportions will be provided for each BMS-986165 treatment group compared to placebo. If expected cell counts are not sufficient for each strata level, then strata levels will be combined for the analysis.

Continuous efficacy endpoints will be analyzed with an ANCOVA model as specified for the primary endpoint in case the endpoint is only collected at one time point. For continuous efficacy

variables that are more frequently collected, a mixed model for repeated measurement (MMRM) method with structured variance covariance matrix specified for the model will be used.

For statistical testing, comparisons of the combined BMS-986165 treatment group response compared to placebo will be performed for the FAS during 52 weeks. There will be no adjustment of the Type 1 error rate for multiple comparisons or testing of multiple endpoints. Nominal p-values will be provided.

[figure not shown]

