#### **4.1.2.2 Randomization Criteria**

Subjects who meet the criteria to continue in Part B and meet the following criteria will be eligible to be randomized to add-on therapy with blinded study treatment:

1.  $< 50\%$  reduction in UPCR from the pre-MMF value (either the value from study screening or historical value before the start of MMF for those already on MMF at the time of screening) to the value at Visit A4. For the subjects who are on MMF at a dose of  $< 1.5$  g/day at the time of screening, the pre-MMF value will be taken from screening
2. UPCR  $\geq 1.0$  mg/mg based on the two 24-hour urine specimens from approximately 7 to 10 days before Visit A4, and just before Visit A4; if the UPCR values differ by  $> 20\%$ , a third 24-hour urine specimen will be collected to determine the average; the third specimen (if needed) should be collected as soon as possible but no more than 10 days after the first two results are reported, as described in [Section 8.4.1](#)

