### 9.3.3 Secondary Efficacy Endpoints

- PRR at Week 24, defined as  $\geq 50\%$  reduction from baseline in 24-hour UPCR
- Complete renal response (CRR) at Week 24, defined as both of the following:
  - 24-hour UPCR  $\leq 0.5$  mg/mg
  - eGFR (using the MDRD equation)  $\geq 60$  mL/min or  $\leq 20\%$  decrease from baseline
- CRR at Week 52
- CRR + successful corticosteroid taper to  $\leq 7.5$  mg/day at Week 24
- CRR + successful corticosteroid taper to  $\leq 7.5$  mg/day at Week 52
- PRR at Week 52

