### 9.4.1 Primary Endpoint Analysis

The analysis of covariance (ANCOVA) for change from baseline in log-transformed 24-hour UPCR at Week 24 will be performed with treatment groups (BMS-986165 3 mg BID, BMS-986165 6 mg BID, and placebo) and randomization stratification factors (24-hour UPCR < 3.0 mg/mg versus  $\geq$  3.0 mg/mg, and total cumulative IV corticosteroid methylprednisolone < 250 mg versus  $\geq$  250 mg) as fixed effects with log-transformed baseline value added into the model as a covariate. Relative treatment differences in percentage change from baseline in 24-hour UPCR at Week 24 on the original scale based on least-square means and the corresponding 2-sided 95% CIs will be provided for combined BMS-986165 treatment groups and placebo. Additionally, least-square means and 2-sided 95% CIs will be provided for the relative difference between each BMS-986165 treatment group and placebo for the FAS.

Prior to unblinding the appropriateness of the log-transformation will be investigated. Further details will be provided in the SAP. For statistical testing, comparison of the combined BMS-986165 treatment group compared to placebo will be performed. There will be no adjustment of the Type 1 error rate for multiple comparisons or testing of multiple endpoints.

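### For the complete-response endpoints, baseline UPCR is adjusted for only as a two-level stratum, which gives up a modest amount of precision

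*Combined protocol and SAP*

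**What the plan says.** **Binary endpoints.** Section 9.4.2 states: "Binary efficacy endpoints (responder/nonresponder) will use stratified Cochran-Mantel-Haenszel (CMH) tests stratified by the factors used for randomization". There are two such factors. One is UPCR, below versus at or above 3.0 mg/mg. The other is "total cumulative IV corticosteroid (methylprednisolone or parenteral equivalent) dose given in the 16 weeks before randomization (< 250 mg versus ≥ 250 mg". That makes four strata. The section promises 95% CIs for differences in proportions but does not say whether these are stratified or adjusted. It also provides: "If expected cell counts are not sufficient for each strata level, then strata levels will be combined for the analysis". No count threshold or merging order is given.

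**Primary endpoint.** Section 9.4.1 fits an ANCOVA with the same two factors, "with log-transformed baseline value added into the model as a covariate".

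**Endpoint definitions.** In Section 9.3.3, CRR has an absolute proteinuria component, "24-hour UPCR $\leq 0.5$ mg/mg", plus an eGFR condition. Partial renal response (PRR) is a "reduction from baseline in 24-hour UPCR" of at least 50%. Four of the six secondary endpoints are built on CRR: CRR, and CRR with steroid taper, each at Weeks 24 and 52.

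**Baseline.** Section 4.1.2.2 requires UPCR of at least 1.0 mg/mg, "based on the two 24-hour urine specimens from approximately 7 to 10 days before Visit A4" and just before that visit. The continuous value is therefore available for every randomized subject.

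**The concern.** An absolute cut-off makes the starting value prognostic by construction: the higher the baseline, the larger the fall needed. Splitting at 3.0 mg/mg captures only part of this. The plan treats continuous baseline as worth adjusting for beyond the strata in the primary analysis, then omits it for CRR without giving a reason.

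At stake is precision. With 78 subjects and few complete responders expected on placebo, chance imbalance in baseline within the lower stratum stays in the estimated CRR difference. Section 9.6.5 says the Week 24 results will help plan later development, so the CRR estimate and its interval are likely to be used. The merging rule could also remove the UPCR split, because it does not say which factor is kept.

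**Working it through.** **1. The plan's own figure.** Section 9.1 gives 88% power at one-sided 0.10 with 52 versus 26 subjects. The effect size and SD are not in the available text, so the figure can only be inverted. Standard error factor: √(1/52 + 1/26) = 0.2402. Implied standardized effect: d = (1.2816 + 1.1750) × 0.2402 = 0.590. No power or response rate is given for the binary endpoints.

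**2. Fall needed for the UPCR part of CRR: 1 − 0.5/baseline.**

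| Baseline (mg/mg) | Fall needed |
|---|---|
| 1.0 | 50% |
| 1.5 | 67% |
| 2.0 | 75% |
| 3.0 | 83% |
| 6.0 | 92% |

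The range from 50% to nearly 83% lies wholly within the lower UPCR stratum.

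**3. What that does to response probability (illustration).** Assume log change is normal and independent of baseline, with placebo mean −0.6 and SD 0.8 (not in the documents). Then P(UPCR ≤ 0.5) = Φ[(ln(0.5/baseline) + 0.6)/0.8].
- Baseline 1.0: Φ(−0.116) = 45%
- Baseline 1.5: Φ(−0.623) = 27%
- Baseline 2.0: Φ(−0.983) = 16%
- Baseline 3.0: Φ(−1.490) = 7%

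For PRR the argument is (ln 0.5 + 0.6)/0.8 = −0.116 at every baseline, so the probability is 45% throughout. Under this model baseline carries no information about PRR.

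**4. Power in simulated trials of 78 subjects.** Assumptions: lognormal baseline truncated at 1.0, median 2.0 to 3.0, log SD 0.5 to 0.7; SD of log change 0.6 to 1.0; placebo mean log change −0.3 or −0.6; effect 0.590 × SD; 30% in the higher steroid stratum, not prognostic; eGFR condition and dropout ignored. There were 18 scenarios per endpoint and 1,500 trials each.

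| Gain from adding log baseline | CRR | PRR |
|---|---|---|
| Over planned CMH, one-sided 0.10 | 1.4 to 6.0 points | 0 to 1.3 points |
| Over a strata-only score test, one-sided 0.10 | 0.6 to 4.4 points | −1.0 to 0.5 points |
| Over planned CMH, one-sided 0.025 | 2.0 to 5.2 points | not used here |

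Example: median baseline 2.5, SD 0.8, placebo mean −0.6, CRR 13% versus 26%. Power is 56.4% with CMH and 60.5% with the covariate.

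**5. How much of that is test size.** In the matching null scenario, rejection at nominal 0.10 was 9.7% for CMH and 10.6% for the covariate score test, a gap of 0.9 points. By the normal approximation, that gap is worth 0.9 × φ(0.161)/φ(1.2816) = 0.9 × 0.394/0.1755 ≈ 2.0 points of power. Of the 4.1-point gain, about 2.1 remain. A further set of simulations gave null rejection of 10.5 to 13.0% for the score test and 8.3 to 11.5% for CMH. With size equalized, about −1 to +2 points were left.

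**6. Precision of the estimate.** The standardized risk difference adjusted for log baseline was unbiased for CRR, with about 2 to 8% less variance than the stratified difference. In CI width: √0.98 = 0.99 and √0.92 = 0.96, so 1 to 4% narrower. In subjects: 78/0.98 ≈ 80 and 78/0.92 ≈ 85.

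**The case against.** The case for leaving the plan alone is substantial.

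- **CMH on the randomization strata is a valid test.** Its null rejection stayed near nominal or somewhat below. Randomization is itself stratified by UPCR, which limits imbalance, and the p-values are nominal. This stands. A reader might infer that the comparison is biased or its error rate wrong; nothing in the documents or the checks supports that.
- **UPCR is not the only adjustment.** The quoted sentence continues to a second factor, IV corticosteroid dose. It would be wrong to say the test uses UPCR alone.
- **PRR does not share the problem.** Its threshold moves with baseline. This stands, and the point is confined to the CRR-based endpoints.
- **The strength of the link is inferred.** The documents do not say that baseline UPCR drives CRR. Section 4.4.2 cites a maintenance trial in which baseline values did not predict long-term outcome, but that is a different outcome and does not bear on a threshold at Week 24 or 52. The prognostic role follows from the definition; its strength is assumed.
- **A logistic model strains sparse data.** Simulated placebo CRR rates were roughly 3 to 21%, or 26 × 0.03 ≈ 1 to 26 × 0.21 ≈ 5 responders. This is a good reason not to replace CMH as the test.
- **Detail may come later.** Section 9.4 leaves complete details to the SAP, and no separate SAP text is available. An adjusted analysis may be planned there; the point concerns what is written here.
- **Merging need not remove the UPCR split.** That is correct: the rule leaves it open, and losing the split is only one possibility.

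**Conclusion.** The point holds as a modest loss of precision on the four CRR-based endpoints. Continuous baseline UPCR is prognostic within strata because of the 0.5 mg/mg cut-off, is already collected, and is already used in the primary analysis. Adding it to the CRR estimate would cut variance by about 2 to 8%.

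The raw power gains in the simulations might tempt a reader to conclude that CMH should be replaced. They do not support that: part of the gain comes from a slightly liberal score test, and what remains at equal size is close to zero or about 2 points.

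The size rests on assumed baseline and change distributions, and on log change being independent of baseline. The power simulations in step 4 also omit the eGFR condition and dropout. The eGFR condition, the nonresponder imputation of Section 9.4.2.1 and the steroid-taper component all create nonresponders for other reasons, so the true gain may be smaller. This is a desirable refinement, not a necessary correction.

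**What to change.** In Section 9.4.2 or the SAP, before the Week 24 database lock:

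1. Keep the stratified CMH as the test for all binary endpoints.
2. For the four CRR-based endpoints, report the treatment difference and 95% CI as a standardized (marginal) risk difference. Obtain it from a logistic model with treatment, both randomization factors and log baseline 24-hour UPCR.
3. Prespecify a fallback for sparse events, for example Firth penalization, and note that it shrinks the difference slightly.
4. State the merging rule for CMH: a count threshold, and collapse the IV corticosteroid factor first so that the UPCR split is kept.
5. Leave the PRR analysis as it is.

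The cost is a few lines of SAP text and some programming, with no extra visits or samples. The downside is reliance on a model and possible instability if very few subjects respond.

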#### **9.4.2.1 Imputation Methods for Secondary [REDACTED] Endpoints**

Nonresponder imputation will be used for the secondary and exploratory binary endpoints, as applicable, for subjects who discontinue early, start a protocol-prohibited medication/therapy that could improve LN, or who have otherwise missing endpoint data at or prior to the specified endpoint.

For continuous secondary [REDACTED] efficacy endpoints that are only collected at one time point, the MI method as described for the primary endpoints will be applied to deal with missing data.

For continuous secondary [REDACTED] efficacy endpoints that are collected more frequently, an MMRM method with unstructured variance covariance matrix specified for the model will be used for handling the missing data.

The efficacy assessment after the start of protocol-prohibited medication/therapy that could improve LN will be considered missing for the statistical analysis and will be imputed as described above.

## 9.5 Safety Analyses

Safety data will be analyzed for treatment-emergent AEs (TEAEs), AEs, SAEs, laboratory analytes, vital signs, and ECGs. Safety will be summarized using the As-treated population during Week 52 [REDACTED]. Categorical data will be summarized as frequency counts and percentages. Continuous data will be summarized using n, mean, standard deviation, median, minimum, and maximum unless otherwise specified.

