## **7.2 Week 24 Subject Status Evaluation**

At Week 24 (Visit B7), investigators should assess, based on their clinical judgment, if continuation in the study remains in the subject's best interest, overall and with regard to progression of renal disease. If the investigator determines that continuation is no longer in a subject's best interest, the subject should stop the study treatment immediately, but if possible, should remain in the study for appropriate follow-up procedures as outlined in Sections 7.3 and 7.4. The investigator will record the reason for discontinuation and will report any AEs or SAEs (see [Section 8.5](#) and [APPENDIX 3](#)).

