## **7.4 Follow-Up After Early Discontinuation from Study Treatment**

In this study, renal response is a key endpoint of the study. Follow-up procedures are of critical importance and are essential to ensuring subject safety and the integrity of the study. Investigators should continue to follow subjects who are discontinued early from the study treatment, for collection of outcome data for 30 days after the final dose of the study treatment, or until death or the conclusion of the study, as required, unless subjects withdraw consent for further follow-up.

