## 9.2 Populations for Analyses

The analysis populations are defined as follows:

Population	Description
Full Analysis Set for Part B	All randomized subjects at the beginning of Part B; following the intent-to-treat principle, subjects will be analyzed according to the treatment assigned at randomization at the beginning of Part B
As-treated Set for Part B	
All randomized subjects who took at least one dose of blinded study treatment at the beginning of Part B; this population will be used for the safety analyses for Part B. Data in this data set will be analyzed based on randomized treatment for Part B, except in the following cases:
 
 
• If a participant received the same incorrect treatment throughout the study, then the participant will be analyzed based on the treatment received
 
• If a participant received study treatment from more than one treatment group, and none of the administrations were consistent with the assigned randomized treatment group, then the participant will be analyzed based on the first treatment received
 

MMF	All subjects who take open-label MMF treatment

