### 9.3.2 Primary Safety Endpoint

Adverse events, vital signs, ECGs, and laboratory abnormalities from baseline through Week 52

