### 9.5.1 Adverse Events

Treatment-emergent AEs, AEs, SAEs, deaths, AEs leading to discontinuation of IP, AEs by maximum severity, and AEs by relationship to IP will be summarized by the Medical Dictionary for Regulatory Activities system organ class and preferred term by (1) treatment arm in Part B and (2) in LTE period for the following 4 treatment groups separately:

- Group 1: BMS-986165 3 mg BID → BMS-986165 3 mg BID
- Group 2: BMS-986165 6 mg BID → BMS-986165 6 mg BID
- Group 3: Placebo BID → BMS-986165 3 mg BID
- Group 4: Placebo BID → BMS-986165 6 mg BID

AEs for combined BMS-986165 3 mg BID (Group 1 and Group 3) and BMS-986165 6 mg BID (Group 2 and Group 4) may also be summarized as described in the SAP.

All TEAEs, AEs, as well as any potential adjudicated AE category will also be summarized by preferred term sorted by decreasing frequency.

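### Part B adverse events through Week 52 are planned as counts and percentages with no person-time denominator or stated at-risk window, so unequal stopping after Week 24 could modestly distort the comparison between arms.

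*Combined protocol and SAP*

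**What the plan says.** The primary safety endpoint in section 9.3.2 is "Adverse events, vital signs, ECGs, and laboratory abnormalities from baseline through Week 52". Safety is analysed on the As-treated set, defined in section 9.2 as "All randomized subjects who took at least one dose of blinded study treatment at the beginning of Part B".

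On the summary measure, section 9.5 states: "Categorical data will be summarized as frequency counts and percentages". Section 9.5.1 presents adverse events by "system organ class and preferred term by (1) treatment arm in Part B". No test or confidence interval is stated for them. Section 8.5 defines a treatment-emergent event by its start relative to the first dose and gives no end to the window.

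On stopping, section 7.2 has investigators judge at Week 24 whether continuing serves the subject, overall and in respect of renal progression. A subject for whom it does not "should stop the study treatment immediately, but if possible, should remain in the study for appropriate follow-up procedures". Section 7.4 asks investigators to follow subjects who stop early "for collection of outcome data for 30 days after the final dose of the study treatment", or until death or the end of the study, as required. Section 7.1 asks for the end-of-treatment visit and the 28-day follow-up visit, with SAEs followed for 30 days after the last dose of IP. Section 8.5.2 ends non-serious event collection at the final study visit, and SAE collection 30 days after the last dose of any study treatment. A note to Table 3 says that randomized subjects who stop IP early stay in the study for follow-up, including Visit B15.

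**The concern.** A crude percentage compares arms fairly only if the arms are observed for similar lengths of time. Here one route out of treatment, the Week 24 evaluation, can depend on efficacy, which is what the trial compares. If the drug works, more placebo subjects may stop for renal progression. If those subjects are then observed for only about four more weeks, the placebo arm has less time in which events can be recorded, and its percentages fall for that reason alone.

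Section 8.5.1 names infections and certain skin events as potential events of interest. Such events can accumulate with time at risk. At equal true rates, the arm observed for longer would show more of them. Because the analysis is descriptive, the risk is that the tables are misread when further development is planned, not that a formal test gives a false positive.

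**Working it through.** **The plan's own figure.** None is given for the safety comparison. The 88% power in section 9.1 concerns the efficacy endpoint and does not bear on this point.

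**The passages on follow-up, side by side.**
- Pointing to continued observation: section 7.1 (subjects who ask to stop must still be followed for the protocol's follow-up procedures), section 7.2 (remain if possible), the Table 3 note (remain, including Visit B15), and the last limb of section 7.4 (until the study concludes, as required).
- Pointing to a short tail: the 30 days in section 7.4, the end-of-treatment and 28-day visits in section 7.1, and the SAE limit in section 8.5.2.
- None says whether four-weekly visits run to Week 52 after blinded treatment stops. The length of adverse-event collection in a subject who stops is therefore not settled by the text.

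**Inputs for the illustration.**
- From the documents: stopping at Week 24, 52-week period, 52 active and 26 placebo subjects.
- From one reading of sections 7.1 and 7.4: observation of about 4 weeks after stopping, hence 28 of 52 weeks.
- Assumed, because the documents give no figures: the share stopping, d, is 35% on placebo and 15% on active. The constant first-event hazard, h, is 1 or 0.3 per person-year (52 weeks taken as one year) and is equal in both arms.

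**Formulas.**
- Observation time, as a fraction of full: (1 − d) + d × 28/52. Placebo: 0.65 + 0.35 × 0.538 = 0.838. Active: 0.85 + 0.15 × 0.538 = 0.931.
- Crude incidence: (1 − d)(1 − e^(−h)) + d(1 − e^(−28h/52)).
- At h = 1 the two bracketed risks are 0.632 and 0.416. Placebo: 0.65 × 0.632 + 0.35 × 0.416 = 0.557. Active: 0.85 × 0.632 + 0.15 × 0.416 = 0.600.
- At h = 0.3 they are 0.259 and 0.149. Placebo: 0.221. Active: 0.243.
- 95% half-width of the difference: 1.96 × √[p_A(1 − p_A)/52 + p_P(1 − p_P)/26].

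| h per year | Placebo | Active | False gap | 95% half-width |
|---|---|---|---|---|
| 1 | 55.7% | 60.0% | 4.3 points | 23.3 points |
| 0.3 | 22.1% | 24.3% | 2.2 points | 19.7 points |

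One placebo subject is 1/26 = 3.8 points. Exchanging the two stopping rates reverses the sign.

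**Exposure-adjusted rates.** Under a constant hazard, expected time at risk to first event is the crude incidence divided by h. Incidence divided by time at risk therefore returns h in both arms: 100 per 100 person-years at h = 1, and 30 at h = 0.3. The false gap disappears.

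**Sensitivity.**
- 50% versus 20% stopping at h = 1 gives 52.4% versus 58.9%, a gap of 6.5 points.
- Counting full observation as 56 weeks (Week 52 plus 28 days), with full-period risks of 10% to 70%, 20% to 50% stopping on placebo and 10% on active, the gap runs from 0.5 to 9.9 points. The 95% half-widths run from about 13 to 24 points.

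**Masking.** On the 56-week window, take a 50% placebo risk and a true hazard ratio of 1.3. With no stopping, active is 1 − 0.5^1.3 = 59.4%, an excess of 9.4 points.
- If 50% of active subjects stop, active is 0.5 × 59.4% + 0.5 × (1 − 0.5^0.65) = 47.8%.
- If 10% of placebo subjects stop, placebo is 0.9 × 50% + 0.1 × (1 − 0.5^0.5) = 47.9%.

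The excess vanishes, while the rate ratio stays at 1.30. This holds only for events unrelated to the reason for stopping.

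**The case against.** Several objections stand in whole or part.

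- *Rates are not ruled out.* Section 9.4 places complete analysis details in a separate SAP, whose text is not available here. A reader might infer that percentages are the only measure the trial will report. The text shows that they will be reported, not that rates are excluded.
- *Subjects are meant to stay.* A reader might infer that collection does end 30 days after stopping. That is one reading among several. Table 5 also lists MMF as a study treatment, so a subject who continues MMF may keep SAE collection open under section 8.5.2. If observation runs to Week 52, the imbalance in time on study computed above disappears.
- *An unaffected comparison exists.* Section 9.6.5 plans safety analyses up to Week 24. Stopping at the Week 24 evaluation cannot alter observation before it.
- *A toxic drug would not simply look safer.* A subject who stops because of an event is already counted with that event, and section 9.5.1 tabulates events leading to discontinuation. Masking is therefore limited to later events, or to events unrelated to the reason for stopping.
- *The proposed rates have assumptions of their own.* They need a roughly constant hazard and non-informative stopping, and stopping for progression or toxicity may be informative.

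A reader might also infer a flaw in the pooled dose summaries, since section 9.5.1 says that "AEs for combined BMS-986165 3 mg BID (Group 1 and Group 3) and BMS-986165 6 mg BID (Group 2 and Group 4) may also be" reported together. The documents do not support that. Groups 1 to 4 are listed for the extension period, nothing says that Part B data are included, and the summary is optional.

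**Conclusion.** The point holds as a modest gap in reporting. In the available text, a primary safety endpoint running to Week 52 has no person-time denominator and no stated at-risk window, while stopping can be related to efficacy and the length of later follow-up is unclear. Distortion is possible but not shown: no stopping rate by arm is given, so its direction is unknown too.

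Under 35% versus 15% stopping at Week 24, four further weeks of observation and equal constant hazards, the distortion is about 2 to 4 points. Across the wider assumed range it stays below 10 points, within the sampling error of 52 versus 26 subjects. No formal safety decision depends on it. It remains worth correcting because it is systematic and easily avoided.

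**What to change.** Keep the counts and percentages. In section 9.5.1, and correspondingly in the SAP, add by arm and for combined BMS-986165 versus placebo:

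- patient-years at risk and exposure-adjusted incidence rates (subjects with a first event per 100 patient-years) with 95% CIs, for TEAEs, SAEs, infections and skin events;
- a stated at-risk window, for example from the first blinded dose to the end of Part B adverse-event collection;
- time on treatment and time on study.

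Separately, sections 7.1 to 7.4, section 8.5.2 and the Table 3 note must be reconciled on how long adverse events are collected after blinded treatment stops. The rates do not resolve that question.

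The cost is some wording and a few tables from dosing, visit and event dates. Because the rates rest on a roughly constant hazard and non-informative stopping, they should supplement the percentages and not replace them.
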